11.4. SAS Code for Efficacy Analysis

11.4.1. SAS Code for Primary Efficacy Analysis Using Bayesian Logistic Regression

The Bayesian logistic regression model is implemented below by SAS PROC BGLIMM. The variable and dataset names are for illustration purpose and may be subject to change:

```
proc bglimm data=adeff nmc=20000      seed=205169;
  class country age_grp vte trt;
  model vte(event='yes') = trt country age_grp / dist=binary cprior=normal(input=priordata);
run;
```

11.4.2. SAS Code for Stratified CMH

The stratified CMH method is implemented by Proc Freq. The variable *event* is a binary indicator, which is used for illustration purpose only.

```
Proc freq data= adeff ;
  tables country*age_grp*trt*event/cmh commonriskdiff;
  ods output cmh=cmh;
run;
```

Signature Page for VV-RIM-00325758 v1.0

Approval/eSignature

01-Dec-2023 18:14:03 GMT+0000

Approval/eSignature

01-Dec-2023 18:33:23 GMT+0000

Approval/eSignature

01-Dec-2023 18:39:46 GMT+0000

Approval/eSignature

01-Dec-2023 18:54:34 GMT+0000

Approval/eSignature

[figure not shown]
01-Dec-2023 19:10:56 GMT+0000

Approval/eSignature

01-Dec-2023 23:03:46 GMT+0000

Signature Page for VV-RIM-00325758 v1.0 Approved

Signature Page for VV-RIM-00325758 v1.0

Approval/eSignature		
		07-Dec-2023 14:24:08 GMT+0000

Signature Page for VV-RIM-00325758 v1.0 Approved

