3.1. Efficacy Analysis Set

The primary analysis will be conducted in the modified intention to treat population (mITT) population, consisting of randomized and treated participants that have either an evaluable venogram, a confirmed episode of venous thromboembolism, or both through day 12. It is based on the treatment allocated (as randomized).

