4.4.2. Secondary Efficacy Variables

- Incidence of major VTE through day 12 (REGN9933 versus enoxaparin). Major VTE includes: proximal DVT; confirmed symptomatic DVT of either leg; confirmed fatal or nonfatal PE including unexplained death for which PE cannot be ruled out
- Incidence of DVT as measured by venography of the operated leg on day 10 ± 2 days (REGN9933 vs enoxaparin)
- Incidence of confirmed, adjudicated VTE through day 12 (exoxaparin vs apixaban)

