5.7.1. Analysis of Primary Efficacy Variable

The primary analysis is to evaluate the efficacy of REGN9933 for the prevention of VTE after unilateral TKA, compared to enoxaparin. The primary efficacy variable is a binary indicator whether a participant has an adjudicated, confirmed VTE through day 12.

For any participant i , let p_i denote the VTE probability, trt_i denote the treatment assignment (0: enoxaparin, 1: REGN9933, 2: apixaban), $country_i$ denote the country indicator (1, 2, .., K), and age_grp_i be the age group indicator (0: $age < 70$ and 1: $age \geq 70$).

The following Bayesian logistic regression model adjusted by stratification factors (country and age group) is specified to compare the event rates of VTE among enoxaparin, REGN9933, and apixaban:

$$logit(p_i) = \beta_0 + \beta_1 * I(trt_i = 1) + \beta_2 * I(trt_i = 2) + \sum_{k=1}^{K-1} \theta_k * I(country_i = k) + \gamma * age_grp_i$$

where β_0 is the log odds of the VTE rate from enoxaparin, β_1 is the log odds ratio of REGN9933 relative to enoxaparin, and β_2 is the log odds ratio of apixaban relative to enoxaparin after adjustment by country and age group. The benefit of the treatment effect of REGN9933 over enoxaparin is expressed in terms of the odds ratio ($=e^{\beta_1}$) that is less than 1.

A weak prior $N(0,0.843)$ is chosen for parameters β_1 and β_2 . With this weak prior, the extreme treatment difference is unlikely, i.e., the probability of the odd ratio between 0.25 and 4 is around 90%. A vague prior $N(0,10^4)$ is used for the other regression parameters.

The treatment effect will be estimated using the Markov Chain Monte Carlo (MCMC) method via PROC BGLIMM in SAS. The SAS code for implementing the Bayesian logistic regression model is provided in Appendix [11.4.1](#)

Bayesian summary statistics (posterior mean and median, and two-sided 90% credible interval) of the treatment effect of REGN9933 vs enoxaparin (odds ratio = e^{β_1}) will be reported.

Based on the logistic regression model, the treatment effect (odds ratio = $e^{\beta_1 - \beta_2}$) of REGN9933 vs apixaban and the treatment effect (odds ratio = e^{β_2}) of apixaban vs enoxaparin will be reported. Their credible interval such as two sided 90% credible interval will also be reported.

The probability-based quantities for the magnitude of treatment effect at thresholds of clinical interest may be provided, e.g., $Prob(OR < 0.5, 0.8, 0.9, \text{etc.} | \text{data})$.

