5.7.3. Sensitivity Analysis

To assess the robustness of the Bayesian model on the choice of prior distributions, sensitivity analyses will be performed and reported for these possible prior distributions for parameters β_0 , β_1 , and β_2 (including but not limited: $N(0,1)$, $N(0,10)$, $N(0,100)$, and $N(0,10^6)$).

A Bayesian logistic regression model with these two covariates (country and treatment group) will be explored to assess the treatment effect conditional on country only.

To assess the sensitivity of the Bayesian logistic model, the stratified Cochran-Mantel-Haenszel (CMH) method by both country and age group will be performed. The SAS code for CMH analysis is provided in Appendix 11.4.2. The stratified CMH by country only as the stratification factor will also be explored.

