5.7.5. Multiplicity Control

As the statistical inference for this study is to focus on estimation rather than testing a formal hypothesis and the Bayesian analysis is performed, the multiplicity adjustments of the different comparisons between groups will not be done.

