11. APPENDIX

11.1. Summary of Statistical Analyses

Table 1: Efficacy/PD Analyses

Endpoint	Analysis Populations	Primary Statistical Method/Analysis	Sensitivity Analysis	Subgroup Analysis	Other Analyses
Primary Endpoint					
Proportions of participants with adjudicated, confirmed VTE through day 12	mITT	Bayesian logistic regression	Stratified CMH analysis	Yes	No
Secondary/PD Endpoints					
Secondary efficacy endpoints	mITT	Bayesian logistic regression	Stratified CMH analysis	Yes	No
aPTT, PT	PDAS	Descriptive Statistics	No	No	No
FXI:C, TGA	PDAS	Descriptive Statistics	No	No	No

Table 2: Safety Analyses

Endpoint	Analysis Populations	Statistical Method	Supportive Analysis	Subgroup Analysis	Other Analyses
Adverse Events	SAF	Descriptive Statistics	No	No	No
Laboratory Measures	SAF	Descriptive Statistics	No	No	No
Vital Signs	SAF	Descriptive Statistics	No	No	No
ECG	SAF	Descriptive Statistics	No	No	No

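### The CMH sensitivity code in SAP 11.4.2 tabulates all three arms, so it cannot return the REGN9933-versus-enoxaparin odds ratio or risk difference, and its tests depend on the apixaban data

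*SAP*

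**What the plan says.** SAP 5.7.1 sets REGN9933 versus enoxaparin as the primary comparison and codes treatment as "0: enoxaparin, 1: REGN9933, 2: apixaban". The Bayesian logistic model uses all three arms and obtains each pairwise odds ratio from its coefficients.

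SAP 5.7.3 then says that, to check that model, "the stratified Cochran-Mantel-Haenszel (CMH) method by both country and age group will be performed". It points to Appendix 11.4.2 for the code and adds that a country-only version will be explored. Table 1 in SAP 11.1 enters "Stratified CMH analysis" as the sensitivity analysis for the primary endpoint and for the secondary efficacy endpoints. Under SAP 4.4.2 the latter include the same day-12 VTE outcome for enoxaparin versus apixaban.

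The code in SAP 11.4.2 is a PROC FREQ step on the dataset `adeff` with the request "tables country*age_grp*trt*event/cmh commonriskdiff". It has no WHERE or BY statement, and its ODS statement saves only the table of CMH tests. The note that the code is illustrative covers the variable `event`, not the arms. No text in SAP 5.7, 5.7.3, 11.1 or 11.4.2 says that the CMH is run on two arms at a time.

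**The concern.** The request puts three treatment rows and two outcome columns in every country-by-age stratum. The Mantel-Haenszel common odds ratio and common risk difference are defined for 2×2 strata, so the code asks for a two-arm quantity from three-arm input. What it can return are association tests across three arms, and these do not address REGN9933 versus enoxaparin alone.

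Protocol 3.2.1 expects apixaban to differ from enoxaparin. An apixaban effect could therefore be read as support for REGN9933, or a REGN9933 effect could be missed. A single call would also return the same result as the check on the primary comparison and on enoxaparin versus apixaban. Finally, `commonriskdiff` is the only between-arm risk difference that either document requests, and as printed it cannot be computed.

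**Working it through.** The plan states no figure for the CMH, so there is none to reproduce.

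**Inputs.** Allocation is 1:1:1 with about 120 per arm, and planning rates are 13% for REGN9933 and 22.4% for enoxaparin (SAP 2.2). Treatment coding is 0/1/2 (SAP 5.7.1). Assumptions: equal arms; 120 evaluable per arm, or 90 because mITT requires "either an evaluable venogram, a confirmed episode of venous thromboembolism, or both through day 12"; apixaban from 22.4% down to 8%, since neither document gives a rate; p<0.05 as a yardstick only.

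**1. What the correlation test compares.** Write x for events by arm (E, R, A), m for total events and N for all participants. With equal arms, each arm expects m/3 events. With scores 0, 1, 2 the numerator is

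0·(x_E − m/3) + 1·(x_R − m/3) + 2·(x_A − m/3) = x_R + 2x_A − m = x_A − x_E.

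REGN9933 drops out, so the 1-df test compares apixaban with enoxaparin.

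**2. Expected counts at the planning rates, apixaban also 22.4%, 120 per arm, unstratified.** Events: R = 15.6, E = 26.88, A = 26.88.

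- 2-df test: m = 69.36 and the expected count is 23.12 per arm. The squared deviations sum to 7.52² + 2×3.76² = 84.83. The event proportion is 69.36/360 = 0.1927. Q = (359/360) × 84.83 / (120 × 0.1927 × 0.8073) = 4.53, p = 0.104.
- Correlation test: x_A − x_E = 0, so p = 1.00.
- Two-arm CMH: m = 42.48, expected 21.24. Q = (239/240) × 2×5.64² / (120 × 0.177 × 0.823) = 3.62, p = 0.057.

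**3. Same REGN9933 and enoxaparin data, different apixaban data.** REGN9933 16/120 and enoxaparin 27/120 are held fixed, in four equal strata.

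| Apixaban | 2-df p | Correlation p | Two-arm p |
|---|---|---|---|
| 4.2% | 0.0002 | <0.0001 | 0.066 |
| 10% | 0.022 | 0.007 | 0.066 |
| 13.3% | 0.088 | 0.056 | 0.066 |
| 17.5% | 0.181 | 0.314 | 0.066 |
| 22.5% | 0.120 | 1.000 | 0.066 |
| 30% | 0.008 | 0.163 | 0.066 |

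The two-arm common odds ratio (0.53) and risk difference (−9.2 points) are the same in every row.

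**4. Share of trials with p<0.05 when REGN9933 = enoxaparin = 22.4%** (exact enumeration of three binomial arms, unstratified).

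| Apixaban | 2-df, 120/arm | Correlation, 120/arm | 2-df, 90/arm |
|---|---|---|---|
| 22.4% | 4.9% | 5.0% | 4.9% |
| 20% | 7.0% | 7.2% | 6.4% |
| 18% | 12.4% | 12.9% | 10.4% |
| 16% | 22.5% | 22.8% | 17.7% |
| 13% | 47.3% | 45.4% | 36.3% |
| 10% | 76.6% | 71.7% | 62.7% |
| 8% | 90.9% | 85.9% | 79.9% |

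The two-arm CMH gives 5.1% (120 per arm) and 4.9% (90 per arm). A simulation of 40,000 trials with 10 strata (assumed 5 countries × 2 age groups) gives 2-df shares of 47.3, 76.7 and 91.1% at apixaban 13, 10 and 8%.

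**5. Missing a REGN9933 effect.** At 13% versus 22.4%, with apixaban at 22.4% and 120 per arm, p<0.05 occurs in 6% of trials for the correlation test, 47% for the 2-df test and 49% for the two-arm CMH.

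**6. What a two-arm run would report at the planning rates.** With 120 per arm, OR = (15.6 × 93.12)/(104.4 × 26.88) = 0.52. SE(log OR) = √(1/15.6 + 1/104.4 + 1/26.88 + 1/93.12) = 0.349, so the 95% CI is 0.26 to 1.03. The risk difference is −9.4 points, with SE √[(0.13×0.87 + 0.224×0.776)/120] = 4.9 points and CI −19.0 to +0.2. With 90 per arm: OR 0.52 (0.235 to 1.14) and −9.4 points (−20.5 to +1.7).

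**The case against.** The appendix code is a sketch. It does not filter to mITT either, and nobody would conclude that mITT was abandoned. SAP 11.4.1 calls variable and dataset names illustrative. The pairs are named in SAP 4.4.2 and 5.7.1, and asking for `commonriskdiff` suggests that two-arm input was intended. A programmer might well run one pair at a time, and a pre-filtered dataset would remove the problem. But the mITT restriction is stated in the text of SAP 5.7, whereas a restriction on arms is stated nowhere. The dataset name is also the one that feeds the three-arm model.

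The correlation result depends on coding. If `trt` were stored as text in alphabetical order, enoxaparin would take the middle score and the test would contrast REGN9933 with apixaban. The 6% in step 5 would become 45%. This stands: the correlation figures hold only for the 0/1/2 coding that the SAP itself defines. In that same scenario the 2-df test, at 47%, loses almost nothing against the two-arm 49%.

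The consequence is also small. SAP 5.7.5 says that "the statistical inference for this study is to focus on estimation rather than testing a formal hypothesis", and no alpha attaches to the CMH. Under SAP 5.7.3 "sensitivity analyses will be performed and reported for these possible prior distributions", and the wide-prior refits already give a nearly data-driven odds ratio for REGN9933 versus enoxaparin. No text promises a risk difference, and SAP 1.3 reports incidence for both arms. All of this stands and limits the weight of the point. It does not make the printed code right, and the refits supply no risk difference.

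**Conclusion.** The code is wrong as written. Run as printed, the named sensitivity analysis gives no common odds ratio and no common risk difference for any pair, and its tests are not a check on REGN9933 versus enoxaparin. With no true difference between those two arms, the 2-df test gives p<0.05 in 5 to 91% of trials at 120 per arm, and 5 to 80% at 90 per arm, as apixaban goes from 22.4% to 8%. The two-arm test stays near 5%. These shares rest on equal arms, assumed apixaban rates and a nominal 0.05 that the SAP does not use. That the tests depend on apixaban does not rest on those assumptions.

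The primary Bayesian estimate and the conduct of the trial are untouched. This should be corrected before database lock, because choosing the arms afterwards would be a choice that the SAP does not pre-specify.

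**What to change.** State in SAP 5.7.3 and 11.4.2 that the CMH, including the country-only version, is run pairwise. Add `where trt in (0,1);` for REGN9933 versus enoxaparin, `where trt in (0,2);` for enoxaparin versus apixaban, and `where trt in (1,2);` for REGN9933 versus apixaban. For each pair, save the Mantel-Haenszel common odds ratio and the common risk difference with their intervals, not only the table of tests. The cost is one WHERE line and one output line per pair in the appendix. It needs no new data and does not change the primary analysis.
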